### 4.3 Subject Inclusion Criteria

A subject will be eligible for participation in the study only if all of the following criteria apply:

- 1) Male or female subject  $\geq 18$  and  $\leq 75$  years of age at screening.
- 2) A female subject is eligible for this study only if she is not pregnant or breast-feeding and one of the following:
  - a. Of childbearing potential but agrees to practice effective contraception, as determined by the PI, or abstinence throughout the study and for 3 months after administration of the last dose of investigational study drug

b. Of non-child-bearing potential

Females of non-child-bearing potential are defined as females with functioning ovaries with a documented history of tubal ligation or hysterectomy or females who are post-menopausal, as defined by 12 months of spontaneous amenorrhea with an appropriate clinical profile, e.g. age appropriate, >45 years, in the absence of hormone replacement therapy. In questionable cases, a blood sample for follicle stimulating hormone and estradiol will be obtained to confirm child-bearing potential.

Acceptable methods of contraception may include a male partner who is sterile prior to the female subject's entry into the study and is the sole sexual partner for the female subject; or 2 or more of the following: 1) implants of levonorgestrel; 2) injectable progestogen, 3) an intrauterine device with a documented failure rate of <1%; 4) double barrier methods including diaphragm or condom with a spermicide.

3) A male subject is eligible for this study only if he is one of the following:

- a. Surgically sterile
- b. Agrees to practice effective contraception (see above) or abstinence throughout the study and for 3 months after the last administration of the investigational study drug

4) Documented diagnosis of HES (history of persistent eosinophilia >1500/ $\mu$ L without secondary cause and evidence of end organ manifestations attributable to the eosinophilia)

5) Signs or symptoms of HES and AEC >1000/ $\mu$ L on stable HES therapy for  $\geq$  1 month at the time of enrollment

6) Participation in protocol 94-I-0079 (Activation and function of eosinophils in conditions with blood or tissue eosinophilia)

7) Agrees to storage of samples for study

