**Participation of Women:**

**Contraception:** The effects of benralizumab on the developing human fetus are unknown. For this reason, men and women of childbearing potential must agree to use adequate contraception (hormonal or barrier method of birth control; abstinence) prior to study entry and for the duration of study participation. Females of childbearing-age must have a pregnancy test result prior to receiving benralizumab. During the course of the study, if a woman becomes pregnant or suspects she is pregnant, she should inform the study staff and her primary care physician immediately.

In the event of pregnancy, the status of the subject and the overall risks and benefits to BOTH mother and fetus with regard to continuing or discontinuing the study agent will be assessed by the PI. The PI will review data that may be available through the manufacturer and that may be in any pregnancy registry. The IRB will also be notified per steps outlined in this protocol.

The investigational drug may be continued if the overall risk and benefit assessment for BOTH the mother and the fetus favors continuation, AND if the subject and the study team agree to this course of action, after a documented informed consent discussion. The IRB and the clinical safety office/sponsor medical monitor will be notified as to the outcome of such a discussion and the subject's decision.

- The pregnant subject will be enrolled in the AstraZeneca pregnancy registry.
- Blood testing will be limited to safety labs, blood draw volumes will be minimized per PI discretion to avoid exacerbation of hemodilution/anemia related to pregnancy.
- The PI will provide the subject with pertinent information to provide to their pregnancy care provider, and will be counseled to consult with a Maternal Fetal Medicine specialist [High Risk Obstetric provider] due to the underlying condition as well as the ongoing study drug exposure.
- All procedures, other than those required for clinical reasons, will be deferred until after the pregnancy.
- The subject will be considered enrolled through at least the end of the pregnancy so as to facilitate collection of outcome data.

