Subjects who have a sustained and complete reduction in eosinophilia and stable clinical signs and symptoms for  $\geq 2$  years and are on a stable dosing interval of benralizumab may be eligible to self-administer study drug monthly or every other month using the FASENRA PEN autoinjector. Subjects who self-administer benralizumab will have a CBC drawn monthly at NIH or a local laboratory. They will return to NIH for routine followup visits every 6 months. An interim visit will be scheduled if they develop clinical symptoms of HES and/or their AEC rises above  $100/\mu\text{L}$ .

Women of childbearing potential will undergo serum pregnancy testing prior to each administration of benralizumab.

At the 22 week visit, subjects who have not received tetanus immunization in the prior 5 years and have no contraindication to Tdap immunization will receive Tdap vaccine. The vaccine will be administered by a study nurse in the OP11 clinic according to standard clinical protocol (0.5 mL intramuscularly).

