## 6.5 Follow-up

Follow up visits will be scheduled daily for 3 days, every 7 days ( $\pm 2$  days) for 4 weeks, every 14 days ( $\pm 3$  days) for 8 weeks after the initial dose of benralizumab vs. placebo and after the first open-label dose of benralizumab. Subsequent visits will be scheduled every 4 weeks ( $\pm 4$  days, up to Week 48) for the remainder of the study for responders and at 12 weeks intervals for non-responders. Subjects going on to the open-label extension (after Week 48) will be scheduled every 4 weeks post last study drug administration ( $\pm 7$  days). After a minimum of 2 years in complete remission, subjects may be scheduled every 8 weeks post last study drug administration ( $\pm 7$  days) and/or every 6 months for subjects self-administering benralizumab using the auto-injector (FASENRA PEN).

The following studies will be performed at every followup visit until (and including) week 48:

- Vital signs, including weight
- Targeted history and physical examination
- AE/SAE assessment
- CBC with differential
- Routine chemistries (electrolyte, hepatic and mineral panels)
- LDH
- Creatine Kinase (CPK)
- Serum tryptase level
- Urinalysis
- Collection of urine (only up to Week 48), serum and plasma for research studies

The following additional studies will be performed at the monthly visits until (and including) week 48, prior to administration of study drug:

- ESR, CRP
- Total Protein
- Uric Acid
- Serum pregnancy testing for women of child-bearing potential
- Serum for PK and ADA studies

The following studies will be performed at monthly/bimonthly/every 6 month visits after week 48:

- Vital signs, including weight
- Targeted history and physical examination
- AE/SAE assessment
- CBC with differential
- Routine chemistries (electrolyte, hepatic and mineral panels; only at NIH visits)
- Serum pregnancy testing for women of child-bearing potential

NOTE: if the subject is receiving drug under an OHSRP-approved reliance agreement or by an outside physician during the COVID19 epidemic, these studies may be performed at the outside site. Subjects receiving drug every 8 weeks will continue to have monthly CBC performed at the NIH or an outside site for 24 weeks after the dosing interval increase.

The following additional studies will be performed at the 12, 24, 36 and 48 week followup visits, and every 4-6 months on the open-label extension except as indicated:

- PT/PTT (week 12 only)
- Troponin (yearly after week 48)

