Subjects who have a sustained and complete reduction in eosinophilia and stable clinical signs and symptoms for  $\geq 2$  years and are on a stable dosing interval of benralizumab may be eligible to self-administer benralizumab using the FASENRA PEN autoinjector. After subjects undergo training in the use of the autoinjector by credentialed OP8 or LPD nursing staff and are provided with FASENRA PEN Instructions for Use (see Appendix F), FASENRA PEN autoinjectors will be provided to the study subject in a cold transport box or sent by the NIH Pharmacy to the subject's home. Subjects will be instructed to obtain monthly CBC (with results sent to the study team) and to contact the study team within 24 hours of each injection to report the date, time, and site of the injection as well as any adverse events. Followup visits will occur every 6 months unless clinical signs or symptoms develop or the AEC rises to  $>100/\mu\text{L}$ , in which case an interim visit will be arranged.

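### The serum pregnancy test required before every dose has no matching schedule for women who self-inject at home, and the two contraception statements end at different times

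*Combined protocol and SAP*

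**What the plan says.** **Testing.** Section 6.4 sets a general rule: "Women of childbearing potential will undergo serum pregnancy testing prior to each administration of benralizumab". It comes directly after the paragraph on self-administration, under which long-term complete responders "may be eligible to self-administer study drug monthly or every other month using the FASENRA PEN autoinjector". For these subjects the same section says "They will return to NIH for routine followup visits every 6 months" and "Subjects who self-administer benralizumab will have a CBC drawn monthly at NIH or a local laboratory". Section 6.7 repeats the visit interval ("Followup visits will occur every 6 months unless clinical signs or symptoms develop", with a raised eosinophil count as a further trigger for an interim visit) and the monthly CBC. Section 6.5 places serum pregnancy testing in a list introduced by "The following studies will be performed at monthly/bimonthly/every 6 month visits after week 48". In the extension, Appendix B marks the test under the 6-month and 12-month columns.

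**Contraception.** Inclusion criterion 2a in Section 4.3 asks for effective contraception in the PI's judgement, or abstinence, "throughout the study and for 3 months after administration of the last dose of investigational study drug". Its examples are a sterile sole partner, or at least two of implant, injectable progestogen, IUD and double barrier. The Participation of Women text that follows asks for "adequate contraception (hormonal or barrier method of birth control; abstinence) prior to study entry and for the duration of study participation". It mentions no second method and no period after the last dose.

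**The concern.** A woman who self-injects and attends every visit and blood draw that Sections 6.4, 6.5 and 6.7 schedule for her will still take most of her doses without the test that Section 6.4 says comes before each one. This is more than a missing detail, because following the schedule breaches a stated safeguard.

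The stake is safety. The protocol says the effects of benralizumab on the human fetus are not known. It makes continued dosing in pregnancy depend on a risk-benefit assessment and a documented consent discussion, and neither can begin until a pregnancy is recognised. On the visit schedule alone, several doses could come first. The autoinjector part has no fixed end date.

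The contraception statements are a smaller, separate matter: site staff and subjects can read two different end dates. Neither issue affects the primary endpoint, the power or the significance level.

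**Working it through.** The plan gives no figure on this point, so there is none to reproduce. The check is a comparison of passages and a count.

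**1. Testing on home dosing**

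| Item | Value | Source |
|---|---|---|
| Test rule | before each administration | 6.4 |
| Home dosing interval | monthly or every other month (4 or 8 weeks) | 6.4, 6.7 |
| Visits while self-injecting | every 6 months | 6.4, 6.5, 6.7 |
| Pregnancy test after week 48 | listed at visits | 6.5 |
| Laboratory test between visits | monthly CBC only | 6.4, 6.7 |

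I take 6 months as 24 to 26 weeks, count a dose falling on the visit day once, and let one scheduled test cover one dose. Doses per visit interval are the visit interval divided by the dosing interval, rounded up:

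- 4-week dosing: 24/4 = 6; 26/4 = 6.5, so up to 7. Without a scheduled test: 6 − 1 = 5 to 7 − 1 = 6.
- 8-week dosing: 24/8 = 3; 26/8 = 3.25, so up to 4. Without a scheduled test: 3 − 1 = 2 to 4 − 1 = 3.

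Per calendar year, with 2 scheduled tests, 12 monthly doses leave 12 − 2 = 10 without one, and 6 every-other-month doses leave 6 − 2 = 4.

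**2. Who is affected**

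Up to week 48, Section 6.5 puts the test at the monthly visits, before study drug is given. In the extension, subjects dosed in clinic are tested at their monthly or every-other-month visits under the same section. The mismatch therefore arises only when dosing moves away from visits, that is, with the autoinjector.

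**3. Contraception end date**

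- A responder's last dose before the extension is at week 44: Section 3.1 gives six further 4-weekly doses from week 24 (24, 28, 32, 36, 40, 44), and Appendix B agrees. The final visit is at week 48 (Section 6.6).
- Participation of Women text: contraception is stated to week 48, which is 48 − 44 = 4 weeks after the last dose.
- Section 4.3: 3 months after the last dose, about 13 weeks.
- Difference: 13 − 4 = about 9 weeks, for a responder who does not enter the extension.
- For comparison, a non-responder last dosed at week 20 and followed to week 48 has 48 − 20 = 28 weeks of participation after the last dose. That exceeds 13 weeks, so no gap arises.

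**The case against.** The strongest reply is that nothing is strictly contradictory. Section 6.5 says what happens at visits; it does not say that testing happens only there. The general rule in 6.4 could simply apply in addition, using the monthly local blood draw that already exists. On this reading only the logistics are missing. Part of this stands: a reader might infer that the pre-dose test is impossible on home dosing, and the documents do not go that far. What they do show is that no section provides for the test between visits, while 6.4 and 6.7 spell out the CBC that is required then.

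A reader might also take Appendix B as proof that no test occurs between visits. It is weak evidence. Its extension columns mark the CBC only every 6 and 12 months too, although 6.4 and 6.7 require it monthly, and the text of the footnote on the pregnancy-test row is not in the available extract. The conflict rests on 6.4, 6.5 and 6.7.

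On contraception, a reader might infer that a woman using one method satisfies one statement and violates the other. Section 4.3 does not support that: it leaves effectiveness to the PI and offers its list as examples. Nor does the Participation of Women text tell anyone to stop early. The two durations are nested, so following Section 4.3 satisfies both.

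There are also mitigations. Subjects must report a known or suspected pregnancy at once, and self-injectors must contact the team within 24 hours of each injection. These help, but they are not a test before the dose. Finally, the group is small: women of childbearing potential, among at most 20 subjects, who reach the autoinjector after at least 2 years of sustained response. That limits the scale and does not remove the mismatch.

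**Conclusion.** The testing mismatch holds. For women of childbearing potential on home dosing, about 5 to 6 of every 6 to 7 doses at 4-week dosing, or 2 to 3 of every 3 to 4 at 8-week dosing, have no scheduled serum test, against a rule requiring one before each. The count assumes a visit interval of 24 to 26 weeks, one test covering one dose, and no interim visit. An interim visit for symptoms or a raised eosinophil count might add a test, but neither trigger is tied to dosing or pregnancy. It does not extend to clinic-dosed subjects.

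The contraception point holds in a narrower form. The end dates differ, by about 9 weeks for a responder last dosed at week 44 who leaves at week 48, taking 3 months as 13 weeks. The descriptions of acceptable methods also differ, softened by the PI's discretion and the illustrative list.

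The sponsor should correct both. They concern safety procedures and leave the statistical analysis untouched.

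**What to change.** Reconcile Sections 6.4, 6.5, 6.7 and Appendix B so that one stated pregnancy-test schedule applies to home dosing and can be carried out as written. Reconcile inclusion criterion 2a in Section 4.3 with the Participation of Women text, so that there is one contraception end date and one description of acceptable methods. Which testing rule and which contraception rule stand is for the sponsor to decide; this review takes no position on either.

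The cost is amendment wording. If the pre-dose rule is kept for home dosing, there is also an added assay for the few women concerned and a wait for its result before each home dose.

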## 6.5 Follow-up

Follow up visits will be scheduled daily for 3 days, every 7 days ( $\pm 2$  days) for 4 weeks, every 14 days ( $\pm 3$  days) for 8 weeks after the initial dose of benralizumab vs. placebo and after the first open-label dose of benralizumab. Subsequent visits will be scheduled every 4 weeks ( $\pm 4$  days, up to Week 48) for the remainder of the study for responders and at 12 weeks intervals for non-responders. Subjects going on to the open-label extension (after Week 48) will be scheduled every 4 weeks post last study drug administration ( $\pm 7$  days). After a minimum of 2 years in complete remission, subjects may be scheduled every 8 weeks post last study drug administration ( $\pm 7$  days) and/or every 6 months for subjects self-administering benralizumab using the auto-injector (FASENRA PEN).

The following studies will be performed at every followup visit until (and including) week 48:

- Vital signs, including weight
- Targeted history and physical examination
- AE/SAE assessment
- CBC with differential
- Routine chemistries (electrolyte, hepatic and mineral panels)
- LDH
- Creatine Kinase (CPK)
- Serum tryptase level
- Urinalysis
- Collection of urine (only up to Week 48), serum and plasma for research studies

The following additional studies will be performed at the monthly visits until (and including) week 48, prior to administration of study drug:

- ESR, CRP
- Total Protein
- Uric Acid
- Serum pregnancy testing for women of child-bearing potential
- Serum for PK and ADA studies

The following studies will be performed at monthly/bimonthly/every 6 month visits after week 48:

- Vital signs, including weight
- Targeted history and physical examination
- AE/SAE assessment
- CBC with differential
- Routine chemistries (electrolyte, hepatic and mineral panels; only at NIH visits)
- Serum pregnancy testing for women of child-bearing potential

NOTE: if the subject is receiving drug under an OHSRP-approved reliance agreement or by an outside physician during the COVID19 epidemic, these studies may be performed at the outside site. Subjects receiving drug every 8 weeks will continue to have monthly CBC performed at the NIH or an outside site for 24 weeks after the dosing interval increase.

The following additional studies will be performed at the 12, 24, 36 and 48 week followup visits, and every 4-6 months on the open-label extension except as indicated:

- PT/PTT (week 12 only)
- Troponin (yearly after week 48)
- ESR, CRP (yearly after week 48)
- Total Protein (yearly after week 48)
- Uric Acid (yearly after week 48)
- Serum B12 (yearly after week 48)
- Quantitative immunoglobulin levels (including IgE)
- HbA1c (12 and 24 weeks only)
- ECG (yearly after week 96 unless clinically indicated)
- Echocardiogram (yearly after week 96 unless clinically indicated)
- Pulmonary function testing including spirometry with response, evaluation of lung volumes and diffusion capacity bronchodilator (yearly after week 96 unless clinically indicated)
- Additional clinical testing as determined by pattern of clinical involvement
- Tissue biopsies of affected organs (if clinically indicated)
- Bone marrow aspirate and biopsy (at 12 weeks only), including

- quantification of eosinophils, mast cells, and their precursors
- assessment of mast cell activation status (CD69 and CD63 surface expression)
- assessment of IL-5R expression on eosinophils, basophils and their precursors
- viable storage of bone marrow mononuclear cells for future studies
- Collection of 60 cc whole blood for isolation and storage of plasma and PBMC for research studies (yearly after week 96)
- Collection of serum for immunologic analyses
- Collection of urine for immunologic analyses (until and including week 48)
- Whole blood flow for IL-5 receptor expression, enumeration of basophil numbers and activation (at weeks 0, 12, 24, 36, 48 only)
- Assessment of T/B/NK cell subsets
- T and B cell receptor rearrangements (weeks 12 and 48 only)

Tetanus antibody titers will be assessed at 22 (pre-immunization) and 28 weeks (post-immunization).

## **6.6 Final Study Visit/Early Termination Visit**

The final study visit will occur 48 weeks after the first dose on study drug (either benralizumab or placebo). The studies to be performed are listed in Section 6.5.

Subjects who are not eligible to continue receiving benralizumab, who elect not to participate in the open-label extension, or who withdraw for any reason prior to completing the study will be asked to return for followup visits every 4 weeks until week 12 (with a scheduled visit at week 12 included) and every 12 weeks thereafter for the planned duration of their study participation.

## **6.7 Open-label Extension**

For subjects who complete the study and for whom benralizumab appears to provide sustained clinical benefit, drug may be provided on an open-label extension until regulatory approval and commercial availability of the marketed drug to prescribing physicians (for HES) or until AstraZeneca ceases development of the drug in HES. All subjects continuing to receive drug monthly on the open-label extension will be scheduled for followup visits and drug administration every 3 months at the NIH. Intervening monthly followup and drug administration will occur either at the NIH or at a collaborating site under an OHSRP-approved reliance agreement. All collaborating sites will submit a local context form and be approved by the NIH IRB prior to site initiation.

Subjects who have a sustained and complete reduction in eosinophilia for  $\geq 2$  years may be eligible to extend the dosing interval to 8 weeks at the investigator's discretion. If at any time following extension of the dosing interval to 8 weeks, the eosinophil count rises

and/or symptoms worsen, the dosing interval may be reduced to every 4 weeks for that subject for the duration of the study. Subjects will be asked to fill out weekly patient-reported outcome questionnaires to assess pain, fatigue, dyspnea and gastrointestinal symptoms (PROMIS v1.0; <http://www.healthmeasures.net>) for 2-4 weeks prior to and 4 months following the change to every 8 week dosing to assist in the objective determination of symptom worsening.

Subjects who have a sustained and complete reduction in eosinophilia and stable clinical signs and symptoms for  $\geq 2$  years and are on a stable dosing interval of benralizumab may be eligible to self-administer benralizumab using the FASENRA PEN autoinjector. After subjects undergo training in the use of the autoinjector by credentialed OP8 or LPD nursing staff and are provided with FASENRA PEN Instructions for Use (see Appendix F), FASENRA PEN autoinjectors will be provided to the study subject in a cold transport box or sent by the NIH Pharmacy to the subject's home. Subjects will be instructed to obtain monthly CBC (with results sent to the study team) and to contact the study team within 24 hours of each injection to report the date, time, and site of the injection as well as any adverse events. Followup visits will occur every 6 months unless clinical signs or symptoms develop or the AEC rises to  $>100/\mu\text{L}$ , in which case an interim visit will be arranged.

